Adjuvant medications for Procedure 1 include: Clonidine 0.1 mg QID (MDD=0.4 mg), clonazepam 0.5 mg QID (MDD=2.0 mg), prochlorperazine 10 mg QD, trazodone 100 mg HS, and zolpidem 10 mg HS. Clonidine will be held if blood pressure falls below 90/60 mm Hg at any visit's vitals check. Adjuvant medications will be offered for one week following administration of XR-NTX as needed for persistent withdrawal symptoms.

If opioid use occurs in combination with missed doses of naltrexone, a naloxone challenge will be administered to confirm that the next dose of oral naltrexone will be tolerated; if necessary, an additional day of adjuvant medication only will be given. In patients at risk for greater withdrawal symptoms (e.g.

history of severe withdrawal, more severe dependence (> 6 bags per day), or a strong reaction to the first dose of naltrexone), the procedure may be slowed down by 1 or 2 days. Once a patient has tolerated a first daily dose of naltrexone 25 mg, he/she is eligible to receive XR-NTX 380 mg IM on Day 5.

Procedure 2:

Design

Patients will undergo a modified outpatient buprenorphine-clonidine-naltrexone procedure to initiate treatment with XR-naltrexone (XR-NTX). During a 10-day procedure, oral naltrexone will be very slowly titrated upwards to the full dose of oral naltrexone but buprenorphine will remain at the same dose of 4 mg a day starting on Day 2. At the end of the procedure, participants will receive the injection of XR-NTX, and the second XR-NTX injection will be administered 4 weeks later. No buprenorphine will be given beyond Day 10.

Rationale

We hypothesize that a gradual titration of naltrexone while maintaining stable doses of buprenorphine will allow for a transition from an opioid agonist to an opioid antagonist state with minimal withdrawal severity. Based on our extensive experience administering low-doses of naltrexone we believe that repeated administration of very low-doses of naltrexone with 1-day dosing interval should not precipitate severe withdrawal. Because of the long-duration of receptor binding naltrexone will accumulate at the receptor and over time it will replace the buprenorphine at the receptor.

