In this procedure, opiate-dependent patients are stabilized briefly on the partial opiate agonist buprenorphine. During subsequent administration of naltrexone and throughout the detoxification, withdrawal symptoms are treated with clonidine, an alpha-2- adrenergic receptor agonist which reduces sympathetic nervous system output produced by opiate withdrawal, clonazepam, a benzodiazepine which reduces the anxiety and dysphoria and permits sleep, and other prn medications such as trazodone or zolpidem for insomnia. Opiate withdrawal causes agitation, elevated pulse and blood pressure and other signs of sympathetic arousal, and sometimes confusion. Clonidine may produce somnolence or hypotension. Clonazepam commonly may produce somnolence. The procedure is conducted in a setting equivalent to a day hospital, with a study physician present at all times, to permit close monitoring of vital signs and mental status.

Naltrexone does not provide a blockade for other substances of abuse, such as cocaine, benzodiazepines, or alcohol. Thus, patients remain at risk of experiencing intoxicating effects and/or overdose with these drugs. This risk is highlighted in the consent form. Rare cases of allergic pneumonia following depot administration have been reported. Patients are advised of this in the consent form and are urged to contact

staff immediately if they develop any trouble breathing. We have observed two cases of allergic hives in patients treated with naltrexone. This risk is highlighted in the study consent form.

The risks associated with buprenorphine administered to participants stabilized on naltrexone are relatively low. Naltrexone will block the majority of mu-opioid effects (Gerra et al., 2006) and therefore: 1) risk of sedation and other adverse effects related to mu-opioid receptor-mediated effects is low, and 2) it is unlikely that physiological dependence will be produced.

Buprenorphine will be dispensed daily during the induction phase, and weekly after administration of the first XR-NTX injection. Buprenorphine will be dispensed by medical staff trained in the use of opioids, and in the management of adverse effects of opioids. The doses proposed for use in the current application are rather low as compared to doses used in the treatment of opioid addiction.

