The use of buprenorphine in opioid-abusing, opioid-dependent volunteers is also associated with the risk of using the medication for the purposes of achieving euphoria. If sublingual buprenorphine is crushed and used parenterally, there is an increased risk of adverse effects but, again, all acute effects should be blocked by naltrexone. Participants will be warned of this risk and advised not to use the medication in this manner. Such an event, if it were to occur, would be short-lived and not life threatening. If it is determined that patients have been abusing their buprenorphine in such a manner, they will be removed from the study and transferred to methadone maintenance. Deaths have occurred in patients who were either injecting, or taking massive oral sublingual doses of buprenorphine in combination with benzodiazepines. It is also likely that the benzodiazepines were injected in those cases. We will monitor participants for evidence of benzodiazepine abuse and remove from the study if clinically indicated.

Risks of Relapse

Treatment with buprenorphine is also associated with a high risk of relapse (Raistrick et al. 2005), and a remote risk of opioid overdose if the patient uses a significant amount of opioids after losing tolerance. Risk minimization procedures include exclusion of patients with a history of overdose in the past three years, regular monitoring of urine toxicology and opioid use, and referral for agonist treatment or inpatient detoxification if relapse occurs.

Side Effects of Naltrexone

Naltrexone has been associated with reversible hepatocellular injury indicated by elevated liver enzymes when administered at doses substantially greater than the 50mg per day dose recommended for maintenance treatment of opiate dependence and proposed for the present studies. When used in the recommended dose range in opiate-dependent patients, this risk is remote (Brahen et al., 1988). Naltrexone is therefore contraindicated in patients with acute hepatitis or liver failure, and such patients are excluded from the study. Patients with hepatic enzyme levels greater than 3 times the upper limit of normal are therefore excluded. Liver enzymes will be repeated at regular intervals over the 8-week treatment course. LA naltrexone achieves higher blood levels than oral naltrexone initially, but these should remain lower than levels associated with hepatitis.

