If naltrexone-induced hepatitis were to occur in the setting of depot, where the naltrexone would be only very slowly eliminated, this would prolong exposure to the offending agent. However, the experience with long-acting injectable naltrexone also suggests it is safe. In our studies with long-acting naltrexone several patients experienced elevation in liver enzymes, which were determined to be related to hepatitis C. One patient in the depot naltrexone trial developed diabetes mellitus, which was deemed unlikely to be study related.

During the outpatient detoxification phase of the study, patients will have daily doses of oral naltrexone supervised at **the clinic**. If a patient misses one or more oral naltrexone doses and resumes regular opiate use, then taking a dose of naltrexone will precipitate opiate withdrawal, which may be quite severe. Patients will be warned not to take the naltrexone if they have missed their dose for more than three days in a row and resumed opiate use for more than one day. They will be told that the reaction could resemble that experienced during the initial buprenorphine-clonidine-naltrexone procedure. Patients will be advised to report to **the clinic** for clinical assessment by a study physician. If history and urine toxicology findings suggest a lapse or possible relapse, a naloxone challenge may be necessary. If the naloxone challenge is positive (withdrawal is precipitated), then the patient will be managed according to guidelines described above (see section entitled Handling of Lapses and Relapses).

Relapsed patients who cannot resume naltrexone are referred for inpatient detoxification or outpatient buprenorphine or methadone maintenance. Self-administration of large doses of opiates may override the blockade produced by naltrexone, resulting in opiate overdose with its attendant risks including respiratory depression and death. Patients will be warned of the severe danger of trying to override the blockade. Also patients who have stopped naltrexone for several days and resume opiates will not be tolerant initially, so that the quantities of opiates self administered prior to treatment, when they were tolerant, may be quite dangerous in the non-tolerant state. Patients will be warned of this. Patients with a history of drug overdose in the past 3 years will be excluded.

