### **Study Objectives and Endpoints**

The primary objective of this pilot open-label study is to evaluate three new outpatient pharmacological procedures to facilitate transition onto a long-acting, injectable form of naltrexone 380 mg (XR-NTX).

The primary aim is to test the feasibility, safety, and effectiveness of the new methods to improve tolerability of naltrexone induction and reducing attrition during detoxification and the first month of naltrexone treatment.

The primary endpoint is the receipt of the two injections of XR-naltrexone given first after completion of the detoxification and induction procedure and the second administered 4 weeks later.

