## **Study Outcome Measures**

### Procedure 1 and Procedure 3

Primary Outcome measure is the measure of XR-naltrexone initiation success defined as the receipt of two consecutive injections of XR-naltrexone.

### Procedure 2

Primary Outcome measure is the measure of detoxification and XR-naltrexone induction success defined as the receipt of the first injection of XR-naltrexone.

Safety of the proposed procedures will be evaluated using a structured instrument for obtaining treatment-emergent adverse effects.

Additional assessment will include measures of residual opioid withdrawal during treatment.

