## **Study Analysis**

The primary analysis is a summary statistic of the percent of participants who initiate treatment and receive two consecutive XR-naltrexone injections (Procedures 1 and 3) or the percent of participants who complete detoxification and receive the first XR-naltrexone injection.

In addition, a percentage of patients that received the second injection among those that receive the first injection will also be calculated (Procedure 1 and 3). A summary of the adverse events and serious adverse events will also be presented

Baseline demographic characteristics will be summarized. For continuous variables, descriptive statistics (n, mean, SD, and range) will be provided. For categorical variables, patient counts, and percentages will be provided.

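### Safety is in the primary aim, but the SAP plans no summary of the liver enzymes and blood pressures that the protocol collects and acts on

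*SAP*

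**What the plan says.** The SAP (Study Objectives and Endpoints) sets the scope: "The primary aim is to test the feasibility, safety, and effectiveness of the new methods to improve tolerability of naltrexone induction". Study Outcome Measures gives the safety method: "Safety of the proposed procedures will be evaluated using a structured instrument for obtaining treatment-emergent adverse effects". Study Analysis gives the output: "A summary of the adverse events and serious adverse events will also be presented". The only other descriptive statistics there come straight after "Baseline demographic characteristics will be summarized" and name no on-treatment variable. These sections do not mention liver enzymes, laboratory values, vital signs or blood pressure.

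The protocol treats two measurable harms as important enough to act on.

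- **Liver.** Side Effects of Naltrexone describes hepatocellular injury and says "Liver enzymes will be repeated at regular intervals over the 8-week treatment course". An enzyme value above 3 times normal delays the next injection (Patient Monitoring and Removal from Study). A value above 5 times normal is a reason for withdrawal after detoxification (Criteria for Early Discontinuation).
- **Blood pressure.** Risks of the Buprenorphine-Clonidine-Naltrexone Procedure states "Clonidine may produce somnolence or hypotension". The adjuvant-medication paragraphs, for Procedure 1 and again for Procedures 2 and 3, state "Clonidine will be held if blood pressure falls below 90/60 mm Hg at any visit's vitals check". Vital signs are taken at the start and end of each induction visit, and they continue after induction (Assessment Instruments).

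**The concern.** An adverse-effect interview finds what a participant notices or is asked about. A raised enzyme or a low reading may come with no complaint. The SAP does not name its instrument. The only structured treatment-emergent measure in the protocol's Assessment Instruments is the SAFTEE, a 3-minute weekly rating, so it might be completed only once during Procedure 1's 5-day induction.

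No text available to this review says that crossing an enzyme or blood-pressure limit is recorded as an adverse event. If the SAP is followed exactly, the report could therefore show no hepatic or hypotensive finding although the protocol's own limits were crossed and acted on. That would weaken the safety conclusion, which is one of the three components of the primary aim.

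A second issue is how such data should be summarised. Entry allows AST or ALT up to just under 3 times normal, and in the investigators' earlier long-acting naltrexone studies "several patients experienced elevation in liver enzymes, which were determined to be related to hepatitis C". A bare count above 3 times normal would not separate pre-existing liver disease from change on treatment.

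**Working it through.** **1. The plan's own figure.** The SAP's only design figure reproduces: 3 procedures × 10 = 30. The protocol requires 15 completers from 30 enrolled, which is 15/30 = 50%. There is no alpha, power or event rate to reproduce, because the analysis is descriptive.

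**2. Data collected against analysis planned.**

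| Harm named in protocol | Data collected | Limit acted on | SAP summary |
|---|---|---|---|
| Liver injury | Liver enzymes | >3 and >5 times normal | None |
| Hypotension | Vital signs, twice per induction visit, then post-induction | <90/60 mm Hg | None |
| Side effects in general | Structured instrument | – | Adverse-event tabulation |

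**3. Illustration of what could be missed.** All rates here are assumptions. Let p be the chance that a participant crosses a limit, s the share of crossings with reportable symptoms, and n the number of participants. Assume independence, and that symptomless crossings are not logged.

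P(at least one crossing, none reported) = (1 − ps)^n − (1 − p)^n

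| n | s | p = 5% | p = 10% |
|---|---|---|---|
| 10 | 25% | 0.9875^10 − 0.95^10 = 28% | 0.975^10 − 0.90^10 = 43% |
| 10 | 50% | 0.975^10 − 0.95^10 = 18% | 0.95^10 − 0.90^10 = 25% |
| 30 | 25% | 0.9875^30 − 0.95^30 = 47% | 0.975^30 − 0.90^30 = 43% |
| 30 | 50% | 0.975^30 − 0.95^30 = 25% | 0.95^30 − 0.90^30 = 17% |

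If staff log every crossing, each of these falls to zero.

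**4. What a table of counts could establish.** With no case seen, the exact two-sided 95% upper limit is 1 − 0.025^(1/n): 30.8% for n = 10, 21.8% for n = 15 and 11.6% for n = 30. The table would describe what happened. It could not exclude a sizeable rate.

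**5. Denominators.**

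- *Liver.* The timing is stated in three ways: before the second injection (Study Visits), at baseline and end of study (Blood and other Biological Samples), and at regular intervals over 8 weeks (Side Effects of Naltrexone). With 15 completers required from 30 enrolled, end-of-study samples could be missing for about half.
- *Blood pressure.* Induction lasts 5 days in Procedure 1 and 10 days in Procedures 2 and 3, with weekday visits. If Day 1 is a Monday, that is 5 visits × 2 = 10 readings against 8 visits (Days 1–5 and 8–10) × 2 = 16. A longer induction gives more chances to record a low value.

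**The case against.** The strongest reply is that these cases are not lost. The adverse-event tabulation is not restricted to the structured instrument. A nurse collects safety measures and asks about side effects at each visit. Enzymes above 3 times normal lead to a delayed injection, a hepatitis panel and repeat tests. Reasons for early removal go on the End-of-Study Form, and clonidine is held at the stated pressure. The trial is a 30-person descriptive pilot, and the protocol calls the liver risk at recommended doses remote. Most of this stands: the gap lies in analysis and reporting, and a large safety analysis would be out of proportion. It does not close the gap, because the SAP analyses neither removal reasons nor held doses, and no available text turns a limit crossing into an adverse event.

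Four stronger readings are tempting, and the documents do not support them.

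- *Participants are not monitored for these harms.* They are; the protocol sets out the measurements and the actions.
- *Crossings will go unreported.* Only *can* is justified, since staff may log them.
- *Clonidine exposure differs twofold between inductions.* Standing doses are 0.1 mg × 4 = 0.4 mg a day in Procedure 1 and 0.1 mg × 2 = 0.2 mg a day in Procedures 2 and 3. But as-needed doses in Procedures 2 and 3 may reach the same 0.4 mg maximum, and the non-randomised SAP plans no comparison between procedures.
- *Each completer has a fixed number of liver panels.* The three timing statements do not settle a number.

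**Conclusion.** The concern holds as a reporting gap. Two harms named in the protocol, with three numeric limits between them, have no planned summary, although safety is in the primary aim. The SAP's stated method can miss symptomless crossings. How often is unknown: the 17% to 47% range rests entirely on assumed crossing and symptom rates, and on symptomless crossings not being logged. It shows that the possibility is not negligible, and it is not an estimate for this trial. The primary endpoint, the sample size and the monitoring of individuals are unaffected. The change should be made before the safety results are written, because it is cheap and uses existing data. The conclusion rests on the sections available to this review, which include the SAP's outcome and analysis sections.

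**What to change.** Add to the SAP's Study Analysis one descriptive safety table, by procedure and overall, with no test between procedures.

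- **AST/ALT.** Give the number with a baseline and at least one post-injection value, as denominator. Show the shift from baseline category to worst post-baseline category, using the protocol's own boundaries: within normal, above normal up to 3 times, above 3 up to 5 times, and above 5 times. Under the entry limit only the first two baseline rows should be filled. Add the number of injections delayed for enzymes.
- **Blood pressure.** Give the number of participants with any reading below 90/60, from the first induction dose through the week after the first XR-NTX injection, when adjuvant medication is still offered. Show the baseline value, the number of visits or readings as denominator, and the number with clonidine held. Take the baseline from screening, because clonidine is already offered at the consent visit before Day 1.
- **Rule.** Report every limit crossing whether or not an adverse event was recorded.

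Before this, the sponsor must reconcile the three protocol statements on liver-test timing, because they set the liver denominator and what a worst value means.

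The cost is some SAP wording and slightly more programming. Liver denominators will be smaller than the number enrolled, and the table should show this. No new data collection, sample size change or change to any clinical rule is needed.

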## **Study Analysis**

The primary analysis is a summary statistic of the percent of participants who initiate treatment and receive two consecutive XR-naltrexone injections (Procedures 1 and 3) or the percent of participants who complete detoxification and receive the first XR-naltrexone injection.

In addition, a percentage of patients that received the second injection among those that receive the first injection will also be calculated (Procedure 1 and 3). A summary of the adverse events and serious adverse events will also be presented

Baseline demographic characteristics will be summarized. For continuous variables, descriptive statistics (n, mean, SD, and range) will be provided. For categorical variables, patient counts, and percentages will be provided.
